9.4 Device Deficiencies

All device deficiencies related to the identity, quality, durability, reliability, safety, or performance of an investigational medical device shall be documented throughout the clinical investigation and appropriately managed by the Sponsor. Device deficiencies include malfunctions, use errors, and inadequate labeling.

10 SOURCE DOCUMENTATION, CASE REPORT FORMS AND DATA MANAGEMENT

Data in this study will be collected on Case Report Forms (electronic or paper) as well as electronic file transfers.

10.1 Source Documents and Case Report Forms

The investigator or his/her designee at each site is responsible for recording investigation-related data onto the CRFs and maintain source documentation supporting the data. Good Clinical Practice in the documentation on source documents and CRFs will be followed. For source documentation or if paper CRFs are used, the data must be legibly written in ink. If changes are required, a single line is to be drawn through the incorrect information, the correct information written in and the change initialed and dated by the individual making the change. The reason for correction may be noted, unless obvious. Pencil, correction fluid or correction tape must not be used and incorrect information must not be obscured (scribbled-out).

The investigator must review, sign, and date the CRFs as indicated on the form or electronically; these responsibilities cannot be delegated to another person. It is the investigator's responsibility to comply with regulatory requirements including, but not limited to, the maintenance of accurate, complete and current records relating to the CRFs.

Data clarification forms (DCFs) may be generated by Senseonics (or designee) or by the monitor during a monitoring visit. DCFs are treated as CRFs and are completed and signed by the investigator or designee.

The Sponsor (or their designee) will review the data against the original source documents and ensure any noted discrepancies are resolved by the investigational site. Subject data

will be compared to information originally recorded on source documents related to the trial (i.e. professional notes, laboratory reports, investigation-specific worksheets, etc.).

Investigation-related information collected on CRFs will be entered into a secure database. The database design and installation will be validated prior to use.

Validation techniques used by Senseonics are consistent with applicable regulations and guidelines. Each database must pass a series of standard tests that demonstrate the usability and correctness of the database system to approved specifications. The test process generates detailed test result logs, which are provided as part of the database documentation.

The details of data review, database cleaning and data querying are described in a Data Quality and Management Plan (DQMP). This plan is updated throughout the investigation as amended data management requirements and investigation-specific data conventions are determined.

A comprehensive EDC User Guideline will be developed for participating investigational sites describing general instructions on CRF completion; this guideline also includes investigation-specific data entry, and query management instructions.

Data entered by investigational sites will be reviewed by the Sponsor or their designee on an ongoing basis to ensure adequate query resolution and identify and query adverse events, protocol deviations, and any other ambiguous data points.

10.2 Glucose Measurement Data Flow Process

10.2.1 Data Logging

The Transmitter is a rechargeable, external device worn over the Sensor insertion site that supplies power to the Sensor. The Transmitter periodically (usually every 5 minutes) reads sensor data and calculates sensor glucose and trends. The information from the Transmitter is then transmitted for display to a handheld device (e.g. Smartphone) via Bluetooth Low Energy with AES-CCM encryption. At any one time, the Transmitter contains all of the data collected since last erasure, extending back in time to the limit of its capacity. Each Sensor reading is recorded with a timestamp. Successive uploads from a subject's assigned Transmitter can be assembled into a cumulative time profile, using these timestamps.

10.2.2 Data Retrieval

Data from Subject Assigned Transmitters will be collected at clinic visits. The data will be downloaded by a data communication device running Senseonics' custom software

application and saved to a file. The file will be uploaded to a 21CFR11 compliant record, utilizing a 21CFR11- compliant third party software application.

The Senseonics' software application will identify the Sensor serial number and ask the user to enter the site ID, subject ID and visit number. The file name will include these identifiers as well as the download date and time. Transmitter data will also be uploaded to a data management system to monitor calibration compliance.

Incomplete or missing data downloads that cannot be used in the analysis or cannot be made available at a future visit would be considered missing data for the purpose of analysis for the corresponding time interval.

10.2.3 Reference Glucose Analyzer Data

Plasma glucose data will be recorded by a YSI Analyzer and recorded on Source Document Forms. This data will be transferred to a 21CFR11-compliant electronic record system. Paper strip records and/or electronic records collected from the YSI Reference Glucose Analyzer will be retained according to GCP. Printouts should be labeled, including a patient identifier, sample number, and operator initials, and either photocopied or scanned.

10.2.4 Blood Glucose Meter Data

Data from the study Subject SMBG Meters will be uploaded at clinic visits and electronically transferred to a 21CFR11-compliant electronic record system.

Incomplete data downloads that cannot be used in the analysis or cannot be made available at a future download would be considered missing data for the purpose of analysis for the corresponding time interval.

During and/or at the conclusion of the investigation, original data from the laptop at the clinical site will be transferred to a 21CFR11-compliant electronic record system. The clinical site will be provided a master CD/USB of the electronic data to meet record retention requirements.

11 STATISTICAL METHODS

11.1 Statistical Analysis Overview

11.1.1 General Considerations

The statistical analysis of the data is focused on assessing performance via downloads and data from the clinic including the Fingerstick Blood Glucose Meter Data (Subject SMBG), the YSI Reference Glucose Data, the Senseonics CGM System Data, and other manual entries (

e.g. Implant Time , Subject Number). Descriptive statistics will be used to summarize all subject Baseline and outcome data collected during the study. Continuous variables will be summarized using means, standard deviations, and ranges. Categorical variables will be summarized in frequency distributions.

Statistical analyses will be performed by validated software (e.g., MATLAB and SAS® 9.4). Adequate source document verification and/or audit activities will be utilized to assess the validity of investigation conclusions. Copies of databases used to prepare clinical report summaries will be archived to enable any statistical analyses performed to be replicated.

11.1.2 Randomization and Data Pooling across sites

Subjects will not be randomized. Subjects will be selected consecutively (i.e., selecting every subject in the order they present at the site) among those who meet the inclusion/exclusion criteria. All subjects will receive sensors and transmitters. The primary effectiveness endpoint (MARD) will be analyzed with data pooling across sites. Site effects will be examined, but only descriptively.

11.1.3 Sensor Evaluation Period

The Senseonics CGM System performance will be evaluated in the period after insertion. The Transmitter will assess the Sensor's signal sensitivity in real time for any premature failure independent of the expected lifetime based on time from insertion. If the measurement of potential degraded response of the Sensor optical system signal drops below a pre-defined percent of its original value and/or systemic patterns in Sensor accuracy to entered calibration points drops below a pre-defined threshold, then the device has reached its end of life (sensor retirement) and will no longer provide glucose readings. This end of life determination marks the end of the accuracy evaluation period for this Sensor. The distribution of times between Sensor insertion and end of life or completion of scheduled study visits, whichever occurs first will be summarized.

11.1.4 Expected Paired Points by Range*

The expected number of paired YSI/sensor points by YSI glucose range are as follows:

YSI range	Each Day 1, 7, 14 16 Hr. Session	Each Day 30,60,90 12.5 Hr. Session	Total
40-60 mg/dL	166	106	815
61-80 mg/dL	446	285	2194
80-120 mg/dL	1128	722	5550
121-160 mg/dL	1078	690	5303
160-200 mg/dL	712	456	3505
201-250 mg/dL	620	397	3052
251-300 mg/dL	290	186	1426

301-350 mg/dL	127	81	623
350-400 mg/dL	65	42	319
		Total paired points	22786

*Estimates based on 66 sensors. Number of YSI values in each range will be approximately half the number of paired points.

11.1.5 Evaluable Data for Analysis

All data will be evaluable for the study safety and effectiveness analysis.

11.1.6 Analysis Populations

Effectiveness Analysis population: The effectiveness analysis and exploratory effectiveness endpoints will be based on all data from all subjects in this investigation with at least one paired glucose reading (one Sensor with one reference glucose). The Senseonics CGM System and reference readings are compared by pairing each reference reading with the first Sensor reading that occurred up to 5 minutes after sample acquisition.

Safety Analysis Population: Safety analysis will be based on all subjects that undergo the sensor insertion in this investigation.

Dexamethasone Analysis Population: The approximately 6 subjects with Sensor's inserted will constitute the dexamethasone analysis population to determine if and when a peak dexamethasone level occurs. Subsequent to determining if and when a peak occurs, all subjects with Sensor's inserted will constitute the complete dexamethasone analysis population.

11.1.7 Dexamethasone Analysis

The peak dexamethasone and the timing that the peak dexamethasone occurs will be analyzed descriptively in the subset of approximately 6 subjects. Subsequent analysis of the dexamethasone levels in all subjects will be analyzed descriptively.

11.1.8 Interim Analysis

A planned interim analysis will be performed after all the subjects have completed Visit 6 (day 30 accuracy visit). Only descriptive statistics will be performed. This interim analysis does not feature any stopping rules and has no impact on the collection of the complete follow-up data through 90 days of Sensor use.

11.1.9 Subject Accountability

A Subject Accountability flow diagram will account for all subjects from informed consent through end of study and includes any early explants or withdrawals (Figure 1 in APPENDIX 1).

11.1.10 Study Demographics Analysis

Descriptive statistics will be provided for demographic variables and other baseline characteristics, such as age, gender, race, BMI, diabetes type, insulin therapy, history of ketoacidosis, and history of hypoglycemia.

11.1.11 Tabulation of Investigational Device Deficiencies

11.1.11.1 Transmitter Deficiencies

A tabulation of all reported transmitter device deficiencies will be presented (Table 1 in APPENDIX 1).

11.1.11.2 Sensor Deficiencies

A tabulation of all reported sensor device deficiencies will be presented (Table 2 in APPENDIX 1).

11.2 Safety Endpoints

The safety endpoint is the incidence of device-related or insertion/removal procedure-related serious adverse events (SAEs) in the clinic and during home use through 90 days post-insertion.

An Adverse Event is considered 'related' if the relatedness is categorized as 'possibly related', or 'related'. The assessment of seriousness and relatedness made by the Medical Monitor will be used for analysis. The numbers of SAEs and the percentage of patients with SAEs will be reported for each SAE type that is observed, identified as device-related, procedure-related or unrelated to the study (Table 3 in APPENDIX 1). The count and proportion of patients experiencing at least one device-related or procedure-related SAE will be presented. No inferential statistical analysis will be performed.

Other safety endpoints include:

- Incidence of insertion/removal procedure or device-related adverse events in the clinic and during home use.
- Incidence of all adverse events in the clinic and during home use.
- Incidence of hospitalizations due to hypoglycemia, hyperglycemia or ketoacidosis occurring during home use.
- Incidence of reported hypoglycemic and hyperglycemic events occurring during home use.

For each of the adverse event (AE or SAE) categories above, the numbers of AEs and the percentage of patients with AEs will be reported for each AE type that is observed and be stratified by the target age enrollment categories (Tables 4A-4E in APPENDIX 1). A listing (Table 5 in APPENDIX 1) will be prepared that identifies each patient with a reported AE or SAE, and relevant information including date of onset, severity level, seriousness, relatedness to the device or procedure, classification as anticipated or unanticipated, corrective action(s) taken, and resolution status (resolved or ongoing).

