Causality: The causal relationship should be determined with respect to the investigational device, the insertion or removal procedure, or other study-related procedures.

None: The event is not associated with the device or procedure. There is no relation between the event and the device or procedure.

Possibly Related: The temporal sequence between the device or procedure and the event is such that the relationship is not unlikely or there is no contradicting evidence that can reasonably explain the Subject's condition. There is a possibility of any relation between the event and the device or procedure.

Related: The temporal sequence is relevant or the event abates upon device application completion/removal or the event cannot be reasonably explained by the patient's condition or comorbidities. The event is related or most likely associated with the device or procedure.

Unknown: There is no evidence or relevant data available to assess the relationship between the event and the device or procedure.

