9.3 Adverse Event Reporting

All adverse events (AEs) will be reported by the Investigator and reviewed by the Sponsor in compliance with applicable regulations. Site will follow local IRB reporting requirements for reporting to IRB.

All SAEs must be reported to Sponsor as soon as possible but in no event later than 48 hours after learning of the event. Include Study ID, Study Site, Adverse Event, causal relationship to device and procedure (insertion/removal/other study procedure), seriousness, expectedness, and provide source documentation as soon as available. The AE form of the CRF must be completed within 3 working days of awareness for all SAEs.

All UADEs must be reported to the Sponsor and to the reviewing IRB as soon as possible, but in no event later than 48 hours after the Investigator first learns of the event (21 CFR 812.150(a)(1)). The AE form of the CRF must be completed as soon as possible but no later than 3 working days for all UADEs.

All adverse events classified as possibly related or related to the device or procedure will be reported to Senseonics as soon as possible but no later than 3 days of learning of events.

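### An SAE of unknown causality falls outside the main safety endpoint, and 'procedure-related' carries two meanings in the safety analysis

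*Protocol*

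**What the plan says.** Protocol 9.1 sets out what causality is judged against: "The causal relationship should be determined with respect to the investigational device, the insertion or removal procedure, or other study-related procedures". It provides four grades: None, Possibly Related, Related and Unknown. The last is defined so: "Unknown: There is no evidence or relevant data available to assess the relationship between the event and the device or procedure".

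Protocol 11.2 maps the grades to the analysis in one sentence: "An Adverse Event is considered 'related' if the relatedness is categorized as 'possibly related', or 'related". SAP 4.2.2 and 6.8 repeat that rule. The Medical Monitor's assessment is the one analysed.

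Three further statements in Protocol 11.2 use the mapping, and SAP 6.8 repeats each:

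- The endpoint covers SAEs related to the device or to the insertion/removal procedure.
- Table 3 gives the number of SAEs and the percentage of patients by SAE type, "identified as device-related, procedure-related or unrelated to the study".
- A patient-level summary follows: "The count and proportion of patients experiencing at least one device-related or procedure-related SAE will be presented".

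Protocol 9.3, on what a site must send with an SAE report, asks for the "causal relationship to device and procedure (insertion/removal/other study procedure"). There, procedure includes study procedures other than insertion and removal.

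**The concern.** The collection scheme is wider than the analysis scheme in two places.

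First, Unknown is a grade that the Medical Monitor may assign, but neither document says how to analyse it. The rule for 'related' names two grades and Unknown is not one of them. An event that nobody could assess is then handled like an event assessed and found not to be related. That can only lower the main safety count.

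Second, the word 'procedure' changes scope between sentences. The study includes glucose challenges and long periods of blood sampling, and Protocol 8.2.3 lists serious risks from them. An SAE from one of these is not a device or insertion/removal event, yet it is plainly connected with the study. Where it goes depends on which meaning of 'procedure' the programmer adopts.

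The safety result is a descriptive count with no hypothesis and no margin, so the classification rule largely determines what is reported.

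**Working it through.** **No figure to reproduce.** The plan states no expected SAE rate, margin or power for safety. The check is therefore a mapping of text to text, followed by a simple scale calculation.

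**Step 1: inputs.**

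- Grades and objects of assessment: Protocol 9.1.
- Grades that count as related: Protocol 11.2; SAP 4.2.2 and 6.8.
- Endpoint scope: Protocol 11.2, "The safety endpoint is the incidence of device-related or insertion/removal procedure-related serious adverse events (SAEs").
- Table categories and patient count: Protocol 11.2; SAP 6.8.
- Scope of 'procedure' in SAE reports: Protocol 9.3.
- Who assigns relatedness: Protocol 11.2 and 13.13 (Medical Monitor). Neither section requires an Unknown grade to be resolved.
- Safety denominator: all subjects who undergo insertion (Protocol 11.1.6), planned as 36 (Protocol 11.3.2.2).

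**Step 2: follow each kind of SAE through the rules.**

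| SAE | In the endpoint? | Table 3 category | In the patient count? |
|---|---|---|---|
| Possibly Related or Related to the device | Yes | Device-related | Yes |
| Possibly Related or Related to insertion/removal | Yes | Procedure-related | Yes |
| Unknown for the device or insertion/removal, and not related to any source | No | Only the unrelated category is left | No |
| Related to a challenge or sampling; 'procedure' read as insertion/removal | No | Only the unrelated category is left | No |
| The same SAE; 'procedure' read as in Protocol 9.3 | No | Procedure-related | Yes |

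Row 3 is the Unknown gap. Rows 4 and 5 are the same event under two readings. Row 4 gives a wrong label, because Protocol 8.2 describes the challenges as done solely for the study. Row 5 puts the subject in a device-or-procedure count that no longer equals the endpoint.

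**Step 3: what one subject is worth.** The incidence is x/36, where x is the number of subjects with a counted SAE. Exact (Clopper-Pearson) 95% limits are shown for scale only; the plan calls for no inference.

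| x | x/36 | Exact 95% limits |
|---|---|---|
| 0 | 0.0% | 0 to 9.7% |
| 1 | 2.8% | 0.07 to 14.5% |
| 2 | 5.6% | 0.7 to 18.7% |
| 3 | 8.3% | 1.8 to 22.5% |

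**Step 4: how likely is at least one?** The documents give no rate, so the subject-level probability p of an affected SAE is assumed. The chance of at least one among 36 is 1 − (1 − p)^36:

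- p = 1%: 1 − 0.99^36 = 30%
- p = 2%: 1 − 0.98^36 = 52%
- p = 5%: 1 − 0.95^36 = 84%

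These values show only how the chance grows with p. None of them is a forecast.

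**The case against.** The best defence is that Unknown does have a rule for the endpoint: the plan names the grades that count, and Unknown is not among them. Counting it as related is a conservative convention that neither document requires. Exposure may also be small. Possibly Related is defined broadly, SAEs need source documents, an independent Medical Monitor adjudicates, and Protocol 13.13 leaves the process to a Safety Management Plan that is not available here. All of this is fair and limits how often the gap would matter. It does not say where an Unknown SAE is tabulated, and it does not justify showing one as unrelated.

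A reader might infer that challenge-caused SAEs are lost from the report, or that the plan directs that they be called unrelated to the study. The documents do not support either reading. Leaving them out of the endpoint follows from its definition. The usage in Protocol 9.3 would place them under procedure-related. They also appear in the by-type SAE table, in the all-AE incidence and in the Table 5 listing, which shows seriousness and relatedness. What stands is an undefined term and a patient count that may not match the endpoint.

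A reader might take the zeros in the sample safety tables as the expected SAE rate. They are labelled as sample data and repeat identical figures across age groups. Their 11 subjects at 15.5% imply about 11/0.155 = 71 subjects, not 36. They are placeholders.

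A reader might also see a reporting gap in Protocol 9.3, where the 3-day rule covers only related and possibly related events. All SAEs must reach the sponsor within 48 hours whatever their cause, so that rule does not affect this endpoint.

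The Table 3 shell was not in the text available here. The point rests on the sentences that govern it.

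**Conclusion.** The concern holds in two limited forms.

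- **Unknown grade.** As written, an SAE adjudicated Unknown for the device or the insertion/removal procedure, and not related to either, is excluded from the main safety endpoint and fits no Table 3 category except the unrelated one. Each affected subject who has no other counted SAE moves the endpoint by 2.8 percentage points, assuming the planned 36 inserted subjects. The direction is always downward. How often this would happen cannot be judged from the documents.
- **Meaning of 'procedure-related'.** The endpoint is limited to insertion/removal; the table and patient-count sentences are not. The two meanings must be reconciled before the tables are programmed. This is an inconsistency in definition, not evidence that any SAE goes unreported.

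The plan should be changed, because the main safety result is a small count and the remedy is cheap.

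**What to change.** In Protocol 11.2 and SAP 4.2.2 and 6.8:

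1. State that an SAE adjudicated Unknown for the device or the insertion/removal procedure counts as related in the main safety endpoint, and show the count without such SAEs beside it.
2. Use the term insertion/removal procedure-related in the endpoint, in Table 3 and in the patient count, so that all three describe the same set of events.
3. Report SAEs related to other study procedures (challenges, IV placement, sampling) in their own Table 3 category, outside the endpoint count and not under the unrelated heading.

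The cost is wording in both documents and one further table category, subject to checking the Table 3 shell. Protocol 9.1 to 9.3 already call for the causality data. The effect on the results can go either way. Counting Unknown can make the endpoint slightly less favourable. The consistent wording could remove challenge SAEs from the patient count if 'procedure' is now read as in Protocol 9.3, so the new category should be shown next to that count.
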